7.4 PRIMARY ENDPOINT

This is a prospective, randomised, open label, blinded endpoint (PROBE), active comparator trial and the clinical endpoints are being adjudicated by an IAC in a blinded fashion. The IAC

Charter contains details of the outcome event adjudication criteria. The study will employ a time to first event analysis (using a stratified Cox proportional hazards regression model) and it is assumed that all patients will be observed until first primary endpoint event or until the last patient entered has completed at least six months of treatment (up to an anticipated maximum duration of approximately 30 months for the first patient entered). The trial will be monitored by an independent DMC.

This study is designed to test two safety hypotheses in NVAf patients that have undergone a successful PCI (elective or due to ACS) with stenting and were treatment naïve or were receiving oral anticoagulant treatment (either with warfarin, another VKA or other novel oral anticoagulant) before the procedure.

The primary endpoint, measured from date of randomisation to end of observation period, is:

- Time to first ISTH MBE or CRNMBE

as determined by the IAC. Only positively adjudicated events will be included in the analyses. They will be analysed using the stratified Cox proportional hazards regression model including age group (non-elderly or elderly [<70 or ≥ 70 years old in Japan and <80 or ≥ 80 years old everywhere else]) as a stratifying factor and treatment arm (110mg DE-DAT vs warfarin-TAT and 150mg DE-DAT and 110mg DE-DAT combined vs warfarin-TAT). For the 150mg DE-DAT versus warfarin-TAT comparison, an unstratified model will be applied comparing 150mg DE-DAT versus warfarin-TAT (excluding elderly EU/ROW patients in the warfarin-TAT group). In addition, an unstratified sensitivity analysis of the non-elderly patients only will be conducted.

Models will be fitted for each comparison separately (110mg DE-DAT vs warfarin-TAT and 150mg DE-DAT vs warfarin-TAT). The Breslow method [9] will be used to handle tied failure times.

The primary analysis will be performed under the intention-to-treat framework on the FAS. Patients who discontinue study medication will be followed until the end of the trial for vital status, ECGs, AEs, OEs (including completion of the bleeding questionnaire) and concomitant medications. All patients will be analysed according to the treatment arm to which they were randomised.

Survival time

For those patients with an OE within the analysis period, the survival time will be calculated as:

$\langle \text{date of event} \rangle - \langle \text{date of randomisation} \rangle + 1$

For those patients without an OE within the analysis period, the censored survival time will be calculated as

$\langle \text{censoring date as per below} \rangle - \langle \text{date of randomisation} \rangle + 1$

When centres are informed about the study end, they will schedule EOT visits for those patients that did not already have their EOT visit. As this is the design of the study, those

patient's EOT visits do not relate to any patient conditions. Therefore, for the primary analysis, patients who did not prematurely stop trial medication (as documented on the "termination of trial medication" (TTM) CRF page) will be censored at their EOT visit. If such a patient who did not prematurely stop trial medication as per the TTM CRF page, based on the call of the centre for the EOT visit, has stopped study medication before the EOT, the date of last trial medication intake will be used for censoring purposes (if available), as it was triggered by the information on end of the study. For patients who already had their EOT visit (i.e. those who stopped treatment prematurely according to the TTM CRF page), they will be censored at the date of their final visit. Centres were asked to schedule final visits for any prematurely discontinued patients between 1st Feb 2017 and 30th April 2017. In order to account for patients for whom premature treatment discontinuation occurs rather late during the trial conduct, the first visit which occurs after the date of 1st Feb 2017 will be used to censor these patients.

For patients where this data is not available, the censoring will be based on the date last seen. Dates used in determining the date last seen are:

- Date of EOT visit
- Date of last intake of study medication
- Date of follow-up visit
- Date of last known vital status, if available (including information obtained by a third party, where possible) if patients withdraw from the study [data collected on the vital status form and the TERM page]
- Date of withdrawal of consent by the patient (if applicable)
- Date of death (if a patient dies).
- Date of any event reported on the OE pages of the eCRF or dates confirmed by adjudication

For patients with DTEs and other OEs that include death (see [Section 7.5.2](#)), the date of death will not be used for censoring purposes, but instead will count as an event. In general, if the date last seen coincides with the date of any outcome event reported, this outcome event will be counted for the primary analysis.

These censoring rules determine the "time at risk" for counting of events for the primary analysis.

The robustness of the primary analysis will be assessed by an on-treatment analysis of the TS and the PPS. The same censoring rules as defined above will be used. However, for patients who already had their EOT visit (i.e. those who stopped treatment prematurely), they will be censored at the date of their last trial medication intake plus 6 days. It will also analyse patients by the actual treatment taken.

The censoring rules defined for the on-treatment analysis determine the "time at risk" for counting of events for the on-treatment analysis, i.e. the on-treatment analysis will only count events that occur while a patient is taking study medication (+ REP of 6 days, if study

medication is stopped prematurely before study end). The date of first intake of study medication will be used as the start of the analysis period in this analysis instead of the date of randomisation. Intermittent off-treatment periods will be ignored in cases of any temporary interruptions in study medication.

These analyses will be based on the TS and the on-treatment period.

The proportional hazards assumption will be investigated for the primary analysis only. The following techniques will be used:

- Plotting log (-log (survival function)) against the log of time by treatment group. Parallel curves are consistent with the proportional hazards assumption.

- Adding time-dependent variables to the Cox model
For each variable in the model an interaction term is derived by multiplying by the log of time and adding to the model. Non-significance at the 5% level is consistent with the proportional hazards assumption.

A summary of adjudication will be presented showing the number of investigator-reported OEs along with whether they were positively or negatively adjudicated or whether they were non-assessable. Further analyses will be performed on investigator reported events (i.e. those that are positively and negatively adjudicated). A sensitivity analysis will be performed that includes any non-assessable events into the positively adjudicated MBE/CRNMBE category.

Two safety hypotheses (110mg DE-DAT vs. warfarin-TAT and 150mg DE-DAT vs. warfarin-TAT) will be tested:

1. 110mg DE-DAT is non-inferior to warfarin-TAT with respect to MBE/CRNMBE over the duration of the trial

2. 150mg DE-DAT is non-inferior to warfarin-TAT with respect to MBE/CRNMBE over the duration of the trial.

To control the Type I error rate at a one-sided 0.025 level, a hierarchical procedure for multiple testing will be used to test the above hypotheses. Additional testing for safety and efficacy endpoints will also be included in this hierarchical procedure. The following hierarchical procedure will be applied:

Step 1 – Non-inferiority of 110mg DE-DAT to warfarin-TAT in MBE/CRNMBE is met at the one-sided 0.025 level of significance

Step 2 – Non-inferiority of 150mg DE-DAT to warfarin-TAT in MBE/CRNMBE is met at the one-sided 0.025 level of significance

Step 3 – Non inferiority of 150mg DE-DAT and 110mg DE-DAT combined to warfarin-TAT in DTE and unplanned revascularisation by PCI/CABG is met at the one-sided 0.025 level of significance

Step 4 – Superiority of 110mg DE-DAT to warfarin-TAT in MBE/CRNMBE is met at the one-sided 0.025 level of significance

Step 5 – Non inferiority of 150mg DE-DAT and 110mg DE-DAT combined to warfarin-TAT in DTE is met at the one-sided 0.025 level of significance

Step 6 – Superiority of 150mg DE-DAT to warfarin-TAT in MBE/CRNMBE is met at the one-sided 0.025 level of significance

If any of the steps above fail to meet statistical significance, the testing procedure will stop at that step and subsequent tests will not be performed.

The Non-Inferiority (NI) margin used will be 1.38 (on the relative hazard ratio (HR) scale). See Section 7.6 of the CTP for a clinical justification of this margin. The upper bound of the Wald confidence interval (CI) of the HR of DE-DAT vs. warfarin-TAT (one-sided 97.5%) will be compared to this NI margin for the NI testing.

Kaplan-Meier survival figures will be presented by treatment group/strata and by treatment group.

Frequency counts will be provided showing the number of patients experiencing recurrent events. In addition, the number of events will be presented as follows: the number of initial events, the number of additional events and the total number of events. ISTH MBEs and CRNMBEs will be presented separately and combined in these summaries.

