3.3.4 Removal of patients from therapy or assessments

3.3.4.1 Removal of individual patients

An individual patient is to be withdrawn from the trial if:

- The patient withdraws consent, without the need to justify the decision

Treatment with study drugs should be discontinued if:

- The patient needs to take concomitant drugs that interfere with the investigational product or other study medication(s)
- The patient is no longer able to take trial medication for other medical reasons (e.g. surgery, AEs, or other diseases)
- The patient is persistently noncompliant with study drug administration
- If a patient becomes pregnant during the trial the investigational drug will be stopped, the patient will be discontinued from the trial medication and the patient will be followed up until birth or otherwise termination of the pregnancy. For further

Proprietary confidential information.

© 2016 Boehringer Ingelheim International GmbH or one or more of its affiliated companies. All rights reserved.

This document may not - in full or in part - be passed on, reproduced, published or otherwise used without prior written permission.

information, including the process for follow-up on the outcome of the pregnancy please see [Section 5.2.2.3](#).

- Patients on dabigatran etexilate who are found to have a CrCl <30mL/min during the course of the trial, should have study medication stopped and a parenteral anticoagulant can be started according to local practice (see [Appendix 10.1](#) for switching to a parenteral anticoagulant). CrCl laboratory testing should be repeated as soon as feasible, ideally within 48 hours. If this second measurement confirms a CrCl <30mL the patient should be permanently discontinued from dabigatran etexilate, unless the concomitant clinical condition is expected to allow recovery of the renal function within 7 days from the initial CrCl reduction. A patient should also be permanently discontinued from study drug, if CrCl drops to <30mL/min at two different occasions during the trial
- In the opinion of the Investigator, continuation on the study drug is not in the patient's best interest, if eligibility criteria are being violated, or if the patient fails to comply with the protocol (e.g. non-attendance at trial assessments)
- The patient elects to stop taking study drug (the patient should be encouraged to resume study drug per the protocol).

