- continue to attend regularly scheduled study visits until the trial ends
- conduct only the final visit in person. All other visits would be done over the phone.
- conduct all remaining study visits over the phone
- discontinue participation in remaining trial activities but permit collection of vital status and OEs at the end of the trial.
- discontinue participation in remaining trial activities but permit collection of vital status at the end of the trial.

The patient will be asked to choose the most rigorous follow-up they are willing to comply with.

For patients who withdraw consent no more data on their medical information will be requested, see Section 3.3.4.1.

The site must make periodic documented attempts (approximately every three months) to locate patients who are lost to follow up.

Proprietary confidential information.

© 2016 Boehringer Ingelheim International GmbH or one or more of its affiliated companies. All rights reserved.

This document may not - in full or in part - be passed on, reproduced, published or otherwise used without prior written permission.

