6.2.3 End of trial and follow-up period

6.2.3.1 End of treatment

All patients will remain on study treatment until the last patient entered has completed at least six months of treatment. Based on the number of OEs, the operations committee will declare the end of the trial date and ask that all patients be brought in for their end of trial visit within a certain time period, which will be communicated by the trial team.

The EOT visit should take place for all patients when they discontinue study drug.

Patients who discontinue the study medication early should be registered as “withdrawn” and patients who complete the full treatment period should be registered as completed in the IRT.

After termination of study drug the patient should be switched to an appropriate non study anticoagulant and antiplatelet regimen (if required) according to the local practices. See [Appendix 10.2](#).

Assessments should be performed as mentioned in the [Flow Chart](#).

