6.2.3.4 Vital Status and Outcome Event Collection

It is important to record the vital status and OEs of all randomised patients at the end of the trial.

If a site has difficulty contacting a patient at the end of the trial, site staff should make a minimum of three documented attempts to contact the patient using different methods (i.e. phone, email, certified letter, other). In the absence of reaching the patient directly, alternative approaches which are allowable via local regulations and IRB/IEC should be used to establish vital status (at minimum) and incidence of thrombotic events and major bleeds (where possible).

Proprietary confidential information.

© 2016 Boehringer Ingelheim International GmbH or one or more of its affiliated companies. All rights reserved.

This document may not - in full or in part - be passed on, reproduced, published or otherwise used without prior written permission.

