A2.23	Patients not willing or able to comply with the protocol requirements or considered unreliable by the Investigator concerning the requirements for follow-up during the study and/or compliance with study drug administration, who have a life expectancy less than the expected duration of the trial due to concomitant disease, or who have any condition which in the opinion of the Investigator, would not allow safe participation in the study (e.g. drug addiction, alcohol abuse).	Exclusion criterion 23 met	PPS

Table 6.2: 1 (continued) Important protocol violations

Category/ Code	Description	Example/Comment	Excluded from
B	Informed consent		
B1	Informed consent not given	Inclusion Criterion 4	All
B2	Informed consent given too late or the dates of the investigator's and patient's signatures do not match		None
B3	Informed consent withdrawn	Only applies from the date at which consent is withdrawn.	All
C	Trial medication and randomization		
C1	Incorrect trial medication taken	Medication kit assigned not matching treatment patient was randomised to (e.g. patient randomized to warfarin-TAT but received 110mg DE-DAT)	PPS
C2	Randomisation order not followed	e.g. forced randomization, mis-stratification	PPS
C3	Non-compliance	
Compliance <80% or >120% over the course of the study for dabigatran patients (determined on a visit-wise basis), or time in therapeutic target range for warfarin patients <45% (also on a visit-wise basis). See Section 7.3 for details on compliance calculations. Patients will be flagged if they exhibit non-compliance for two consecutive visits or more (for both dabigatran and warfarin patients).
 
Non-compliance caused by temporary interruption of treatment due to a procedure or a drop in CrCl to less than 30mL/min should not be classified as a protocol violation.
	PPS, but only from start of non-compliance onwards
C4	Trial medication taken at the wrong time	First dose of study drug not administered at the correct time (should be between 6 hours after sheath removal and up to 120 hours post PCI)	PPS
D	Concomitant medication		

Table 6.2: 1 (continued) Important protocol violations

Category/ Code	Description	Example/Comment	Excluded from

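### For patients without the applicable EOT or final-visit date, SAP 7.4 can end bleeding time at risk at last known vital status, so time when bleeding was not ascertained can count as bleed-free

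*SAP*

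**What the plan says.** SAP 7.4 has a main censoring rule and a fallback.

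- **Main rule.** Patients who did not stop trial medication early are censored at the EOT visit. Early stoppers are censored at their final visit, or, to cover late discontinuers, at the first visit after 1 February 2017.
- **Fallback.** "For patients where this data is not available, the censoring will be based on the date last seen". The listed sources are EOT visit, last intake, follow-up visit, consent withdrawal, death, outcome-event dates and "Date of last known vital status, if available (including information obtained by a third party, where possible) if patients withdraw from the study". Because an early stopper needs a final visit, one with an EOT date but no final visit also falls here.
- **Effect.** These rules define the time at risk "for counting of events for the primary analysis", which is time to first ISTH major bleed or CRNMBE.

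SAP 6.6 and Protocol 7.3.1 and 7.4 use similar vital-status wording for patients lost to follow-up.

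The protocol separates survival from bleeding information in two places. The last of five follow-up options in Protocol 6.2.2 is to "discontinue participation in remaining trial activities but permit collection of vital status at the end of the trial"; the option before it adds outcome events. For patients who cannot be reached, Protocol 6.2.3.4 asks sites to "establish vital status (at minimum) and incidence of thrombotic events and major bleeds (where possible"). CRNMBE is not named there.

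**The concern.** A patient known to be alive at a given date is not thereby known to be free of bleeding at that date. If the vital-status date closes the interval, the time since the last bleeding assessment enters the Cox risk set as bleed-free, and bleeds in that time are counted only if someone happens to report them. This lowers the apparent bleeding rate in whichever arm has more such time.

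The rule feeds the non-inferiority tests on bleeding (Steps 1 and 2 of the hierarchy) and the bleeding superiority tests (Steps 4 and 6). The trial is open label, so unequal loss between arms is possible.

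The SAP does not define withdrawal from the study, and the protocol uses the term in two senses. In Protocol 3.3.4.1 the trigger is consent: "The patient withdraws consent, without the need to justify the decision". In Protocol 6.2.3.1 it is treatment: "Patients who discontinue the study medication early should be registered as" withdrawn in the IRT. The size of the fallback group depends on which sense is meant. Nor does the SAP say outright that the latest listed date governs, although a date last seen implies it.

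**Working it through.** **Inputs from the documents.** Margin 1.38 and one-sided 0.025 (Protocol 7.2, SAP 7.4). From Protocol 7.6: 334 events per pair, 834 patients per arm, 14% with an event at one year, uniform accrual over 24 months, follow-up of 6 to about 30 months. **Assumed, because the documents give no figure:** the share f of each arm in the fallback group, and a true HR of 1.0 for power.

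**1. The plan's own figures.** With SE = 2/√334 = 0.1094, power = Φ(ln 1.38/SE − 1.96) = Φ(0.983) = 83.7%, against 83.6% stated. With monthly hazard λ = −ln(0.86)/12 = 0.01257, P(event) = 1 − (e^(−6λ) − e^(−30λ))/(24λ) = 0.199. This gives 166 events per 834 patients and 499 in total, against 167 and about 500 stated.

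**2. One fallback patient.** Suppose bleeding ascertainment stops at a random point in follow-up, vital status is known to trial end and no later bleed is captured. Simulating 2,000,000 patients gives:

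| | P(event counted) | Mean months at risk |
|---|---|---|
| Fully followed | 0.1993 | 15.87 |
| Fallback, vital-status date | 0.1037 | 16.55 |
| Fallback, last ascertainment | 0.1037 | 8.27 |

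**3. One arm.** Rate(f) = [(1−f)·0.1993 + f·0.1037] / [(1−f)·15.87 + f·16.55]. Relative to λ this is 0.994, 0.989 and 0.973 at f = 1%, 2% and 5%.

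**4. Hazard ratio and error.** The HR factor is k = Rate(f dabigatran)/Rate(f warfarin). The error at a true HR of 1.38 is Φ(−ln k/SE − 1.96). For 5%/2%: k = 0.973/0.989 = 0.984, and Φ(0.146 − 1.96) = 0.035. A Cox simulation of the same set-up (834 per arm, 40,000 trials per scenario, Monte Carlo SE 0.0008) is shown beside it.

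| Dabigatran/warfarin | k | Error, formula | Error, Cox | Cox, half of later bleeds captured |
|---|---|---|---|---|
| 1%/1% | 1.000 | 0.025 | 0.025 | – |
| 5%/5% | 1.000 | 0.025 | 0.026 | – |
| 2%/1% | 0.995 | 0.028 | 0.027 | 0.026 |
| 5%/2% | 0.984 | 0.035 | 0.036 | 0.031 |

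With the imbalance reversed, power at HR 1.0 falls from 83.7% to 82.5% (1%/2%) and 79.9% (2%/5%) by formula. The Cox runs give 83%, 82% and 79%.

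**5. Milder assumptions.** If vital status is known on average only halfway to trial end, 5%/2% gives 0.029. With front-loaded bleeding (Weibull shape 0.6), 2%/1% gives 0.027 and 5%/2% gives 0.032. If every later bleed is captured, the current rule is unbiased.

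**6. Bleeds at stake.** 834 × f × (0.1993 − 0.1037) is about 0.8, 1.6 and 4 per arm at 1%, 2% and 5%, out of about 167.

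**7. Cutting at last ascertainment.** Using 8.27 in place of 16.55 gives k = 1.000 in all these scenarios, and the Cox runs give errors of 0.024 to 0.026 and power of 83%. Events and time must be cut together. If later bleeds still count but event-free patients are cut, 2%/5% gives 0.029 (half captured) to 0.034 (all captured).

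**The case against.** The strongest reply is that few patients can be affected, and this largely stands. Patients who stop treatment stay on the visit schedule with the bleeding questionnaire and are asked to accept the most rigorous follow-up they will tolerate (Protocol 6.2.2). SAP 6.6 names full collection of outcome events as a goal. The rule using the first visit after 1 February 2017 keeps late discontinuers out of the fallback. The quoted source is also limited to patients who withdraw; those who merely cannot be contacted enter through the lost-to-follow-up wording.

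Second, the on-treatment analyses in SAP 7.4 censor early stoppers at last dose plus 6 days, which removes the disputed time for them. That helps, but they are sensitivity analyses with a different estimand: they also discard off-treatment follow-up that was properly observed.

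Third, moving known late bleeds, fatal ones included, out of the primary analysis of a bleeding trial fits awkwardly with intention to treat. That is fair, and it is acceptable only if a named sensitivity analysis counts them all.

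A reader might infer more than the documents support:

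- *That consent withdrawals are carried forward as bleed-free.* The SAP's protocol-violation table excludes their data ("Only applies from the date at which consent is withdrawn"), and the consent date is itself a listed source.
- *That censoring at death is wrong.* Outcome events are entered within 24 hours of awareness (Protocol 5.2.2.2), so death is a sound end for a patient still on schedule.
- *That SAP 6.6 and Protocol 7.3.1 and 7.4 are separate errors.* They need their wording aligned with one rule.
- *That no other rule exists.* SAP 7.6, on bleeding outcomes, is redacted, and the analysis-dataset specifications are not visible.

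**Conclusion.** The point holds for a limited group and is minor. Followed as written, SAP 7.4 can count time without bleeding ascertainment as bleed-free for patients who lack the applicable EOT or final-visit date.

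It would be tempting to conclude that the rule favours non-inferiority. The documents do not support that. They give neither the share affected nor its split by arm, so the direction is unknown. Excess loss in a dabigatran arm would help non-inferiority, excess loss in the warfarin arm would hurt it, and balanced loss does essentially nothing.

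The one-sided error of about 0.027 at 2%/1% and about 0.035 at 5%/2% rests on assumed shares, vital status known to trial end and no later bleeds captured. Nothing in the documents suggests a 5%/2% split, and at small shares only a bleed or two per arm is at stake. The case for changing the rule is that it is cheap to state precisely in advance and that it governs a safety endpoint in an open-label trial.

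**What to change.** In SAP 7.4, for fallback patients and the bleeding endpoints only:

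1. Replace last known vital status with the last date bleeding was ascertained. This is a visit or call with the bleeding questionnaire or outcome-event collection, a third-party contact documented as asking about bleeding (whatever the answer), or the date of death if the patient was still on the visit or telephone schedule.
2. Apply that cut-off to events and time at risk alike, in every arm.
3. Keep the current rule as a sensitivity analysis, counting all late-learned bleeds, fatal ones included.
4. Report by arm the number of fallback patients and of late-learned bleeds.
5. Define withdrawal from the study, state which listed date governs, and align SAP 6.6 and Protocol 7.3.1 and 7.4.

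Leave the composites containing death (Steps 3 and 5) unchanged; no calculation here bears on them.

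**Cost.** SAP wording and one derived date; no new data, because an undocumented contact does not count. Person-time lost is f × (16.55 − 8.27) divided by the arm's mean months at risk: about 0.5%, 1.0% and 2.6% at f = 1%, 2% and 5%. At most about 0.8, 1.6 and 4 late-learned bleeds per arm move to the sensitivity analysis. The new rule assumes that loss is unrelated to bleeding risk. If affected patients bleed 1.5 times as often (5%/2%), the simulated HR is 1.40 with complete data, 1.39 under the new rule and 1.37 under the current one.
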